MicroCube, LLC.

4 ABBREVIATIONS & TERMS

| | Table 4-1: List of Abbreviations & Terms |
|-----------|--|
| AE | Adverse Event |
| BMI | Body Mass Index |
| CBC | Complete Blood Count |
| CEC | Clinical Events Committee |
| CFR | Code of Federal Regulations |
| CI | Confidence Interval |
| CIN | Cervical Intraepithelial Neoplasia |
| CIP | Clinical Investigation Plan (Protocol) |
| CRF/eCRF | Case Report Form/Electronic Case Report Form |
| Discharge | Discharge (in the context of the Minitouch procedure): the point at which the subject leaves the site or institution after undergoing the Minitouch procedure |
| EA | Endometrial Ablation |
| EASE | Minitouch E ndometrial A blation Sy stem Treatment for Menorrhagia: An E valuation of Safety & Effectiveness Clinical Trial |
| EC | Ethics Committee |
| EDC | Electronic Data Capture |
| Enrolled | Consented -enrolled: a consented patient that does not proceed to treatment for any reason (such as screen failure, declines treatment or participation) is categorized as consented-enrolled |
| | Treated -enrolled: a qualified patient in whom the Minitouch procedure is initiated is categorized as treated-enrolled |
| FDA | Food and Drug Administration |
| FSH | Follicle Stimulating Hormone |
| GCP | Good Clinical Practice |
| GEA | Global Endometrial Ablation |
| HIPAA | Health Insurance Portability and Accountability Act of 1996 |
| HMB | Heavy Menstrual Bleeding |
| ICF | Informed Consent Form |
| ICH | International Council for Harmonisation of Technical Requirements for Pharmaceuticals for Human Use |
| IFU | Instructions for Use |
| IGE | Investigator Global Evaluation |
| IRB | Institutional Review Board |
| ITT | Intent to Treat |
| IUD | Intrauterine Device |
| IV | Intravenous |
| NIH | National Institutes of Health |
| NRS | Numerical Rating Scale |
| MIQ | Menorrhagia Impact Questionnaire |
| NSAID | Non-steroidal Anti-inflammatory Drug |
| OUS | Outside the United States |
| OPC | Objective Performance Criteria |
| PBLAC | Pictorial Blood Loss Assessment Chart |

Page 12 of 65

CONFIDENTIAL & PROPRIETARY

Page 13 of 65

| Table 4-1: List of Abbreviations & Terms | | |
|--|---|--|
| PGE | Patient Global Evaluation | |
| PE | Physical Exam | |
| PI | Principal Investigator | |
| PN | Part Number | |
| РР | Per Protocol | |
| PRN | As needed / when necessary | |
| QOL | Quality of Life | |
| SADE | Serious Adverse Device Effect | |
| SAE | Serious Adverse Event | |
| SIS | Saline Infused Sonohysterography | |
| SOC | Standard of Care | |
| SOP | Standard Operating Procedure | |
| STD | Sexually Transmitted Disease | |
| UADE | Unanticipated Adverse Device Effect | |
| UK | United Kingdom | |
| ISO 14155 | Clinical investigation of medical devices for human subjects — Good clinical practice | |

CONFIDENTIAL & PROPRIETARY

5 PROTOCOL SYNOPSIS

| Title | Minitouch Endometrial Ablation System Treatment for Menorrhagia: An Evaluation of Safety & Effectiveness | | |
|---|---|--|--|
| Short Title | EASE Clinical Trial | | |
| IDE No. | G180282 | | |
| ClinicalTrials.gov Identifier | NCT04267562 | | |
| Protocol No. & Revision | TD18036 v5.0 | | |
| Version Date | 14Dec2021 | | |
| Study Device | Minitouch Endometrial Ablation System ("Minitouch System") | | |
| Proposed Indications for Use | The Minitouch Endometrial Ablation System is intended for ablation of the endometrial lining of the uterus for the treatment of menorrhagia (heavy menstrual bleeding) due to benign causes in premenopausal women for whom childbearing is complete | | |
| Study Design This is a prospective, multi-center, open-label, single-arm, clinical investigation study Design evaluate the Minitouch Endometrial Ablation System in premenopausal women menorrhagia menorrhagia | | | |
| Study Objective | To evaluate the safety and effectiveness of the Minitouch System | | |
| Study Duration | At least 37 months, including an estimated one month of pre-enrollment assessment and 36 months post-treatment follow up | | |
| Planned Number of Sites | Approximately 10 sites from the United States only | | |
| Planned Enrollment | Up to 126 premenopausal women with menorrhagia | | |
| Primary Effectiveness Endpoint | Percent of patients demonstrating reduction of menstrual flow as evidenced by a Pictorial Blood Loss Assessment Chart (PBLAC) score of \leq 75 at the 12-month post procedure time point | | |
| Study Success | To achieve study success, 12-month success rate should exceed the 66% Objective Performance Criterion (OPC) developed by the FDA, outlined in correspondence of Oct 29, 2015 ⁽¹⁾ | | |
| Primary Safety Measure | Reported rate of device and procedure-related serious adverse events at 12-months post-procedure as adjudicated by the CEC | | |

CONFIDENTIAL & PROPRIETARY

Page 14 of 65

Page 15 of 65

| Secondary effectiveness outcome measures include the following: | | | | |
|---|--|--|--|--|
| | DRIAC: at 6 and 12 months | | | |
| | Monstrual Status at 6 and 12 months categorized by: | | | |
| | Interstrual Status at 6 and 12 months categorized by: | | | |
| | • Amenorrhea: PBLAC score U | | | |
| | ○ Light Bleeding: PBLAC score 0 ≤ 35.0 | | | |
| | • Normal Bleeding: PBLAC score 35.1 to 75.0 | | | |
| | • Eumenorrhea: PBLAC score 75.1 to 99.9 | | | |
| | Menorrhagia: PBLAC score >100 | | | |
| | Patient Global Evaluation (PGE): at 6, 12, 24 and 36 months | | | |
| | Patient satisfaction with treatment | | | |
| | Menstrual status | | | |
| | Recommend to friends | | | |
| | Investigator Global Evaluation (IGE): at 6, 12, 24 and 36 months | | | |
| | Investigator satisfaction with treatment | | | |
| | Menstrual status | | | |
| | | | | |
| Secondary Outcome | Quality of Life Measures: at 6, 12, 24 and 36 months | | | |
| Measures | Improvement of quality of life as measured by: | | | |
| ivicasures | Menorrhagia Impact Questionnaire (MIQ) | | | |
| | Dysmenorrhea-related Numerical Rating Scale (NRS) pain score | | | |
| | Procedure: | | | |
| Procedure-related Numerical Rating Scale (NRS) pain score | | | | |
| The following parameters will also be collected: | | | | |
| | Total procedure time | | | |
| | Total treatment time (total energy delivery time) | | | |
| Total procedure energy in joules | | | | |
| | Anesthesia regimen | | | |
| | • Procedure-related pain at pre-procedure (baseline), discharge | | | |
| | and 24-hours post-procedure | | | |
| | Need for cervical dilation | | | |
| | Secondary safety outcome measures include the following | | | |
| | Any medical surgical intervention to treat abnormal bleeding anytime | | | |
| | following the ablation procedure | | | |
| | Incidence of Adverse Events (AEs) Serious Adverse Events (SAEs) and | | | |
| | Unanticipated Adverse Device Effects (UADEs) at 24 and 36 months | | | |

CONFIDENTIAL & PROPRIETARY

| Qualified participants must meet all of the following inclusion criteria: | | |
|---|-----|--|
| | 1) | Female age 30 to 50 years |
| | 2) | Excessive menstrual bleeding due to benign causes |
| | 3) | Uterine sounding depth measurement of 6.0 - 12.0 cm (external os to internal |
| | | fundus) |
| | 4) | A minimum uterine cavity length of 4.0 cm (internal os to internal fundus) |
| | 5) | A minimum PBLAC score of ≥ 150 for 1 menstrual cycle (obtained during |
| | | screening) and must also have a documented history of excessive menstrual |
| | | bleeding prior to study enrollment |
| | 6) | Endometrial biopsy within 12 months prior to treatment procedure with no |
| | - | abnormal pathology |
| | 7) | Premenopausal at screening as determined by FSH measurement \leq 40 IU/L when |
| | | age is \geq 40 years |
| | 8) | Patient agrees to use a reliable form of contraception during the study, and to |
| | , | follow these requirements: |

| | to anatomic/pathologic weakness or thinning of the myometrium (Classical |
| Evaluaion Critoria | caesarean section and transmural myomectomy are examples of such |
| Exclusion Criteria | treatments that may interrupt the integrity of the uterine wall) |
| | 15) Any general health, mental health or social situation which, in the opinion of |
| | the investigator, could represent an increased risk for the patient, or the |
| | ability of the patient to complete study requirements |
| | 16) Known/suspected abnormal uterine/pelvic anatomy or condition, such as |
| | frozen pelvis |
| | 17) Abdominal, pelvic or gynecological malignancy |
| | 18) Untreated/unevaluated cervical dysplasia, except cervical intraepithelial |
| | neoplasia I (CIN I) |
| | 19) Previous endometrial ablation procedure |
| | 20) Abnormal or obstructed, or perforated cavity as determined by investigator |
| | via standard clinical practices (e.g., hysteroscopy, saline infusion |
| | sononysterography). This includes, but is not inflited to: |
| | a. Septate of bicornuate uterus, arcuate uterus of other congenital |
| | h Bedunculated or submussed myomas distorting the uterine savity or not |
| | fully resected |
| | c Polyns larger than 1 cm |
| | 21) Intramural or subserosal myomas > 3 cm in size, or any myoma that distorts |
| | the uterine cavity |
| | 22) Any patient who is currently participating or considering participation in any |
| | other research of an investigational drug or device |
| | |
| Study Management | MicroCube, LLC or its designee |

CONFIDENTIAL & PROPRIETARY

Page 17 of 65

| Data Management, Safety Review & Clinical Events Committee (CEC) Coordination | Avania [name] |
|---|---|
| Sponsor/Manufactur er | MicroCube, LLC [name] |

Page 18 of 65

CONFIDENTIAL & PROPRIETARY

6 BACKGROUND

Menorrhagia (heavy menstrual bleeding) can have significant negative effects on the quality of life of women including medical complications, anemia, time lost from work, physical discomfort, lifestyle and psychological disruption, and increased health costs.

Hysterectomy has traditionally been regarded as the definitive surgical treatment for menorrhagia. However, despite a 100% success rate (complete cessation of menstruation) and high levels of satisfaction, it is a major surgical procedure with significant physical complications and social and economic costs. This led to "first generation" hysteroscopic endometrial ablation devices that utilize a resectoscope and electro-cautery tools to minimally invasively ablate the functional layer of the endometrium, thus preventing abnormal uterine bleeding.

"Second-generation" GEA devices for ablating the lining of the uterus have been introduced in the market with the aim of providing simpler, quicker, safer, and improved outcomes. These procedures involve destroying the endometrium using radiofrequency energy, heated saline (freely circulating in the uterus), heated fluid inside a balloon, cryosurgery, and microwave energy. On October 29, 2015, the Food and Drug Administration (FDA) issued a letter, "Dear Global Endometrial Ablation Manufacturer", that provided guidance to future global endometrial ablation device manufacturers and explained the basis for an objective performance criterion (OPC):

"Since 1997, the United States Food and Drug Administration (FDA) has approved five non-hysteroscopic global endometrial ablation (GEA) devices based on the results of randomized controlled trials (RCTs) that compared the safety and effectiveness of the GEA device to the same control – hysteroscopic rollerball ablation. Rollerball ablation is an older, well-known surgical technique used to treat heavy menstrual bleeding from benign causes. The study designs that supported the approval of the five GEA devices were very similar. They enrolled between 250 and 350 subjects using either a 1:1 or 2:1 (device: control) randomization scheme and had comparable patient populations. The primary endpoint for all five studies was the reduction in menstrual blood loss measured by the Pictorial Blood Loss Assessment Chart (PBLAC), a validated menstrual blood loss scoring system. One of the inclusion criteria required a baseline PBLAC score of at least 150 or 185, and the individual patient success criteria for effectiveness was defined as a PBLAC score of less than or equal to 75 at one year following the ablation procedure. For all subjects, pretreatment evaluation was performed to confirm the study eligibility criteria were satisfied (e.g., absence of cavity distortions, lesions that might interfere with the GEA therapy). The analysis population consisted of all subjects who presented for their scheduled treatment, having satisfied the study eligibility criteria (intent-to-treat). This analysis population included women who presented for treatment, but did not receive the planned therapy due to reasons such as identification of exclusionary pathology immediately prior to ablation, withdrawal of consent, etc. Patients with missing PBLAC scores at one year following the ablation procedures were considered treatment failures. A study was considered a success if the proportion of successes in the GEA group met a pre-specified non-inferiority margin compared to the proportion of successes in the rollerball ablation control group.

Using a generalized linear mixed model with study as a random effect, the FDA determined that the average success rate across the five GEA devices was 75.6% (65.6%, 83.5%) and 77.2% (66.5%, 85.2%) for the rollerball ablation control. The FDA performed

Page 19 of 65

CONFIDENTIAL & PROPRIETARY

additional analyses to evaluate the effect of baseline covariates on the primary endpoint, including age (above and below 40), baseline PBLAC score (at least 150), uterine sound (6 to 12 centimeters), and presence of fibroids (< 3 cm). Using analysis of covariance methods, the FDA found that none of these baseline covariates had a significant impact on the study results. Based on this analysis, the FDA identified an objective performance criterion (OPC) for the minimum success rate for effectiveness. The OPC is 66% based on the lower bound of the 95% confidence interval of the average success rate for the five approved GEA devices."

The Minitouch System is an endometrial ablation device that is similar in principle to the "second generation" endometrial ablation devices. The EASE Clinical Trial is being conducted to assess the safety and efficacy of the Minitouch System.

6.1 Summary of Pre-Clinical and Clinical Testing (Prior Clinical Experience)

Pre-clinical testing for the Minitouch System demonstrates that the system performs as intended. Tests include the following in which the Minitouch System met the required pre-specified acceptance criteria:

- Design and Performance Verification
- Materials Testing (Biological Safety and Biocompatibility)
- Software
- Electrical Safety and EMC
- Usability
- Environmental & Life Cycle Testing
- Packaging/ Transportation Testing
- Sterilization Validation
- Dose Confirmation and Simulation Studies
- Ex-Vivo Human Uteri Ablation

The Minitouch System has been commercially available outside the United States (OUS) since 2011. As a result, there is extensive clinical experience with the device. Specifically:

- To date, there have been over 4000 real-world clinical procedures completed by more than 180 users at over 70 hospitals/centers predominantly located in the UK. Of these, one (1 or 0.025%) incidence of bowel injury occurred during clinical use. This event was attributed to procedural use errors and the patient was not an optimal candidate for the procedure.
- Additionally, there are over 50 publications (abstracts) reporting the OUS clinical experience of the Minitouch System. A safety analysis (review of all adverse events reported) was conducted.
 - A total sampling of 1,040 patients treated with the Minitouch System were included in the safety analysis.
 - A total of 14 events were reported in the literature and are summarized below. The events were consistent with those expected to occur in patients undergoing endometrial ablation.

| | Occurrence Rate |
|------------------------------------|-----------------|
| Event Description/Terminology | [n (%)] |
| (as reported in the literature) | (where N=1040) |
| Infection (suspected or confirmed) | 5 (0.48%) |
| Post-procedure pain/cramps | 7 (0.67%) |
| Vasovagal episode | 2 (0.19%) |

The Minitouch pre-clinical and clinical data are detailed in the Investigator's Brochure.

Page 20 of 65

CONFIDENTIAL & PROPRIETARY

7 STUDY OBJECTIVE

7.1 Device and Study Rationale

The Minitouch Endometrial Ablation System is designed with the patient and user in mind to expand women's access to menorrhagia treatments that are safe, effective, and a less invasive alternative to hysterectomy.

To provide a benchmark against which to judge the safety and effectiveness of the investigational system, this study is a prospective, single-arm, non-randomized, multi-center clinical trial of the effectiveness of endometrial ablation with the Minitouch System versus the FDA identified OPC for GEA devices. All procedures will be performed using the Minitouch System manufactured by MicroCube. The goal of the current study is to support reasonable safety and effectiveness of the investigational product compared to currently FDA-approved GEA devices.

7.2 Study Objectives

7.2.1 Primary Objective

The primary objective of this study is to demonstrate the safety and effectiveness of the Minitouch Endometrial Ablation System in treating patients with menorrhagia.

The study will demonstrate the Minitouch System's success rate at 12 months post-procedure exceeds the 66% OPC for minimum success rate of effectiveness developed by the FDA.

The Primary Safety Objective is the reported rate of device or procedure-related SAE at 12 months post-procedure. Serious adverse events are expected to be rare (<1%). ⁽⁸⁻¹³⁾

The safety endpoint at 24 and 36-months will include all device or procedure-related adverse device effects, SAEs and UADEs defined in **Section 14 Adverse Event Reporting**.

7.2.2 Secondary Objective

Secondary objectives of this study are to evaluate improvement of quality of life, patient and investigator satisfaction, and the need for medical or surgical intervention to treat abnormal bleeding (as determined necessary by the study investigator) in the 12 months following the ablation procedure.

8 DEVICE DESCRIPTION

8.1 System Overview

The Minitouch Endometrial Ablation System (Minitouch System) is a global endometrial ablation (GEA) device intended to treat menorrhagia by ablating the endometrium of the uterus.

The Minitouch System consists of two main components:

| | Minitouch System Components | Product Number |
|---|-----------------------------------|----------------|
| ٠ | Minitouch Hand Piece (Hand Piece) | 4501 |
| ٠ | Minitouch Generator (Generator) | 4001-01 |

The Generator consists of four (4) main modular components and accessories (Power Cord & Stand Kit):

| | Generator Components | Product Number |
|---|----------------------|----------------|
| • | Central Unit (CU) | 4002 |
| • | Display | 4003 |

Page 21 of 65

CONFIDENTIAL & PROPRIETARY

| | Generator Components | Product Number |
|------------------------------------|----------------------|----------------|
| Inter-cor | nnecting Cable (ICC) | 4004 |
| Keypad | | 4005 |
| Power Cord NEMA 5-15 (US) 4006 | | 4006 |
| Stand Kit | I | |
| • B | ase | 4007 |
| • S | wing Arm | 4008 |
| 0 D | lock | 4009 |

Figure 8-1: Minitouch Endometrial Ablation System

The Hand Piece is a sterile, single-use energy applicator. It is slim, flexible and atraumatic, and designed for transcervical access to the uterine cavity without requiring dilation of the cervix. It is used exclusively with the Generator for delivering microwave energy to the uterine cavity.

The Generator is a non-sterile, reusable, line-powered, modular system intended for generating, delivering and monitoring microwave energy. The Generator is used exclusively with the Minitouch Hand Piece. The Generator software version used in the EASE Clinical Trial is R02-02-02.

The Minitouch System has no gas or fluidic systems or other consumables. Refer to the Instructions for Use for additional details regarding the Minitouch System.

8.2 Principle of Operation

Heavy menstrual bleeding (HMB), also called menorrhagia, can be treated by ablating the endometrial tissue of the uterus. The endometrial lining of the uterus contains most of the endometrial tissue. Additionally, some endometrial tissue may protrude into the myometrium making the endomyometrial

Page 22 of 65

CONFIDENTIAL & PROPRIETARY

junction more of a zone rather than a surface. The endometrial layer and the junctional zone together form the Target Tissue for ablation. The Target Tissue is approximately in the shape of a triangular pillow, with the two cornua and the internal os of the uterine cavity forming its three corners. It is thickest in the mid-uterine section, up to 20mm thick, and tapers off towards the edges and corners. Refer to **Figure 8-2** below.

Figure 8-2: Target Tissue Diagram (Left: Mid Coronal View, Right: Mid Sagittal View)

The goal of the procedure is to safely ablate all of the Target Tissue in order to ensure that no endometrial tissue remains viable after the procedure.

8.3 Proposed Indications for Use (IFU)

The Minitouch Endometrial Ablation System is intended for ablation of the endometrial lining of the uterus for the treatment of menorrhagia (heavy menstrual bleeding) due to benign causes in premenopausal women for whom childbearing is complete.

8.4 Device Instructions

A comprehensive Instructions for Use (IFU) for the Minitouch Endometrial Ablation System, including warnings and precautions, has been created. Please refer to the most current version for complete details on preparation and procedural use of the device.

9 STUDY ENDPOINTS

9.1 Primary Effectiveness Endpoint

The primary effectiveness endpoint is a reduction in menstrual blood loss as assessed by the Pictorial Blood Loss Assessment Chart (PBLAC) data, a validated, patient self-reported menstrual diary scoring system. All patients must have a baseline PBLAC score of \geq 150 with a documented history of excessive menstrual bleeding to document a clinical diagnosis of menorrhagia.

An individual patient will be considered a success if the PBLAC score is \leq 75 at 12 months post-procedure without incidence of additional interventions or treatments for bleeding prior to the 12-month follow-up

Page 23 of 65

CONFIDENTIAL & PROPRIETARY

visit. To achieve study success, the lower bound of the 95% CI of 12-month success rate should exceed the 66% Objective Performance Criterion (OPC) developed by the FDA.⁽¹⁾

9.2 Primary Safety Endpoint

The primary safety endpoint is the incidence of device- or procedure-related serious adverse events at 12months post-procedure. The overall rate and severity of all the reported adverse events will also be documented. Procedure-related serious adverse events are expected to be rare (<1%).⁽⁸⁻¹³⁾

9.3 Secondary Outcome Measures

Secondary effectiveness and safety outcome measures will be assessed at the timepoints described below.

The secondary safety outcome measure at 24 and 36 months will include all device or procedure-related adverse device effects, SAEs and unanticipated adverse device effects (UADE) are defined in **Section 14 Adverse Event Reporting**.

Any medical surgical intervention to treat abnormal bleeding following the ablation procedure is considered a treatment failure. If menstrual status is assessed as "High/Heavy" by the investigator at the 24 or 36-month follow-up, the patient will be considered a treatment failure.

Secondary effectiveness outcome measures will include the following:

Patient Global Evaluation (PGE): at 6, 12, 24 and 36 months

- Patient satisfaction with treatment
- Menstrual status
- Recommend to friends

Investigator Global Evaluation (IGE): at 6, 12, 24 and 36 months

- Investigator satisfaction with treatment
- Menstrual status

Quality of Life Measures: at 6, 12, 24 and 36 months

- Improvement of quality of life as measured by:
 - Menorrhagia Impact Questionnaire (MIQ)
 - o Dysmenorrhea-related Numerical Rating Scale (NRS) pain score

Procedure:

•

- Endometrial ablation procedure-related Numerical Rating Scale (NRS) pain score
 - The following parameters will also be collected:
 - Total procedure time
 - Total treatment time (total energy delivery time)

Page 24 of 65

CONFIDENTIAL & PROPRIETARY

- Total procedure energy in joules
- Anesthesia regimen
- Procedure-related pain at pre-procedure (baseline), discharge and 24-hours postprocedure
- Need for cervical dilation

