10 STUDY DESIGN

This study is a prospective, multi-center, open-label, single-arm, clinical investigation to evaluate the Minitouch Endometrial Ablation System in up to 126 premenopausal women with menorrhagia. The treatment procedure may be performed in an office setting or ambulatory / outpatient surgery centers/operating room (OR).

Candidates will be identified via review of existing patient records and, if necessary, as a result of IRBapproved recruitment advertisements (see **Figure 10-1: Study Execution Diagram**). Study staff will confirm general eligibility and identify already existing SOC (standard of care) testing which may be applied to the trial.

Study staff will obtain written informed consent as outlined in Section 11.5 Informed Consent.

Screening may require more than one visit. The first visit requires documentation of written informed consent and it is recommended that the visit include patient training on the method of collecting PBLAC diary data, a validated patient self-reported menstrual diary scoring system. ⁽²⁾

A subsequent visit may occur after approximately one month, and after completion of the PBLAC diary. The subject will return the completed PBLAC diary and the site personnel will confirm menorrhagia with a PBLAC a score of \geq 150. Then the patient will continue screening for additional eligibility assessments as outlined in **Figure 10-1: Study Execution Diagram** and **Section 12.3 Screening Visits.**

Patient enrollment occurs on the day of the treatment following confirmation of eligibility. Once confirmed, then the patient may undergo the Minitouch procedure. One day after procedure, the study staff will contact the patient to assess the patient's procedure-related pelvic pain level utilizing the NRS (0-10 scale). Every effort should be made to ensure the 24-hour contact is conducted even if the window falls on a weekend. The follow-up visits will occur at 2 weeks, 3 months, 6 months and 12 months, 24 months, and 36 months post-procedure. Total study duration for a Patient is approximately 37 months, including one month of pre-enrollment assessment, and 36 months post-treatment follow up.

CONFIDENTIAL & PROPRIETARY

***NOTE:** Final eligibility must be confirmed by the investigator prior to procedure initiation.

Figure 10-1: Study Execution Diagram

Page 26 of 65

CONFIDENTIAL & PROPRIETARY

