12.9 Durability Visits Conducted 24 and 36 Months (± 8 weeks) After Treatment

The 24 and 36-month visit may be conducted via phone, letter, email or in person as described in Section 12.1.

The 36-month visit is the final study visit. Complete both the 36-Month Visit and the Study Completion eCRFs.

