On a scale of 0 to 10, with 0 being no pain and 10 being the worst pain possible, please mark the appropriate box that best describes your menstrual pain.

| □0 | □1 | □ 2 | □ 3 | □ 4 | □ 5 | □ 6 | □ 7 | □ 8 | □ 9 | □ 10 |
|------|----|-----|-----|-----|---------|-----|-----|-----|-----|----------|
| No | | | | | Moderat | e | | | | Worst |
| Pain | | | | | Pain | | | | | Pain |
| | | | | | | | | | | Possible |

Numerical Rating Scale (NRS) for Procedure-related Pain

On a scale of 0 to 10, with 0 being no pain and 10 being the worst pain possible, please rate your **procedure-related pain** by marking the appropriate box that best describes your pain NOW.

| □0 | □1 | □ 2 | □ 3 | □ 4 | □ 5 | □ 6 | □ 7 | □ 8 | □ 9 | □ 10 |
|------|----|-----|-----|-----|---------|-----|-----|-----|-----|----------|
| No | | | | | Moderat | e | | | | Worst |
| Pain | | | | | Pain | | | | | Pain |
| | | | | | | | | | | Possible |

CONFIDENTIAL & PROPRIETARY

| ATTA GLOE | ACHMENT D: SAMPLE RAT BAL EVALUATION OF SATIS | 'ING SFAC | SCALE FOR PATIEI | NT A TUD | ND USER (INVESTIGATOR) Y TREATMENT | | | | |
|--------------|--|---|------------------------|-------------|---------------------------------------|--|--|--|--|
| Patient Glo | bal Evaluation (PGE) | | | | | | | | |
| Are you | u satisfied with the treatment yo | ou re | ceived for menorrhagi | ia? | | | | | |
| | Very Satisfied | | Satisfied | | | | | | |
| | Not Sure | | Dissatisfied | | Very Dissatisfied | | | | |
| How w | ould you describe your menstru | ial sta | atus? | | | | | | |
| | No Bleeding (Amenorrhea) | | | | | | | | |
| | Spotting | | | | | | | | |
| | Light Bleeding (Hypomenorrh | ea) | | | | | | | |
| | Medium or Normal Bleeding | Medium or Normal Bleeding (Eumenorrhea) | | | | | | | |
| | High or Heavy Bleeding (Men | orrha | agia) | | | | | | |
| Would | you recommend this procedure | e to y | our friends? | | | | | | |
| | Yes | | | | | | | | |
| | No | | | | | | | | |
| Investigato | r Global Evaluation (IGE) | | | | | | | | |
| Are you | u satisfied with the treatment th | nis pa | tient received for mer | norrh | agia? | | | | |
| | Very Satisfied | | Satisfied | | | | | | |
| | Not Sure | | Dissatisfied | | Very Dissatisfied | | | | |
| How w | ould you describe the patient's | mens | strual status? | | | | | | |
| | No Bleeding (Amenorrhea) | | | | | | | | |
| | Spotting | | | | | | | | |
| | Light Bleeding (Hypomenorrh | ea) | | | | | | | |

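### The 24- and 36-month failure rule uses the open-label investigator's bleeding rating and leaves out the patient's own answer to the same item, so durability success could be overstated

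*Combined protocol and SAP*

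**What the plan says.** Protocol section 9.3 states the first route to failure as "Any medical surgical intervention to treat abnormal bleeding following the ablation procedure is considered a treatment failure". The second applies when menstrual status is judged High/Heavy "by the investigator at the 24 or 36-month follow-up, the patient will be considered a treatment failure". No other bleeding-based trigger is given for these visits.

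The same section schedules both raters at the same times: "Patient Global Evaluation (PGE): at 6, 12, 24 and 36 months" and "Investigator Global Evaluation (IGE): at 6, 12, 24 and 36 months". Each evaluation includes menstrual status. Attachment D gives patient and investigator the same five categories, from no bleeding up to High or Heavy Bleeding (Menorrhagia). The Schedule of Events (Table 23-1) confirms both forms at Months 24 and 36.

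On blinding, section 10 says: "This study is a prospective, multi-center, open-label, single-arm, clinical investigation". On the mode of the late visits, section 12.9 says: "The 24 and 36-month visit may be conducted via phone, letter, email or in person".

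Effectiveness at 24 and 36 months is analysed in the ITT cohort (17.1.1), in the per-protocol cohort (17.1.2) and, as treatment success, across the subgroups (17.7). Secondary endpoints are descriptive, with no hypothesis test (17.6).

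**The concern.** At month 12, success rests on the patient's own diary score (PBLAC of 75 or less) together with no intervention. After month 12 the only bleeding rating that can make a patient a failure comes from the investigator, who knows the treatment and may have performed the procedure (13.16). The patient's rating on the identical item is collected at the same visit and then left out of the rule. Nothing in the plan says what happens when the two disagree.

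The case at risk is specific: a woman who marks High or Heavy, whose investigator marks a lower category, and who has had no intervention. Other parts of the plan do not reliably catch her. Lack of effectiveness is not an adverse event, and continued heavy bleeding that has not worsened is treated as pre-existing (14.1.5). The Menorrhagia Impact Questionnaire lets her answer Heavy or Very Heavy, but it too lies outside the failure rule. No diary, physical examination or blood count is scheduled at 24 or 36 months. What is at stake is the durability rate and any statement based on it.

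**Working it through.** **1. Who can become a failure at 24 or 36 months (section 9.3 set against Attachment D)**

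| Intervention for bleeding | Investigator rates High/Heavy | Patient rates High or Heavy | Failure under 9.3? |
|---|---|---|---|
| Yes | either | either | Yes |
| No | Yes | either | Yes |
| No | No | Yes | **No** |
| No | No | No | No |

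Only the third row is in question. Counting the patient's rating as well moves that row alone, so the reported success rate can stay the same or fall.

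**2. Denominator**

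The documents state no figure for durability, so the planned sample size (17.2.1) serves as the denominator. It reproduces. With a null rate of 0.66, an expected rate of 0.78, one-sided alpha of 0.025, 80% power and null variance:

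n = [(1.960 × √(0.66 × 0.34) + 0.842 × √(0.78 × 0.22)) / 0.12]² = 113.26, rounded up to 114, as stated.

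For 10% dropout, 114/0.9 = 126.7, or 127, against the stated 126 (114 × 1.1 = 125.4 rounds up to 126). The difference of one does not matter here.

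**3. Effect of each discordant patient**

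Let d be the number of women in the third row. Then success (investigator-only rule) − success (either rater) = d/n.

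| d | n = 126 | n = 114 |
|---|---|---|
| 1 | 0.8 points | 0.9 points |
| 5 | 4.0 points | 4.4 points |
| 10 | 7.9 points | 8.8 points |

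The number of patients available at 24 and 36 months is not given. With a smaller denominator each patient weighs more.

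**4. A range under assumptions**

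The documents give no discordance rate. Let h be the share of patients with heavy bleeding and no intervention, and s the share of those whom the investigator also rates heavy. Assume that nobody without heavy bleeding is rated heavy. Then overstatement = h × (1 − s).

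- h = 10%, s = 0.9: 1.0 point (about 1 of 126 patients)
- h = 20%, s = 0.8: 4.0 points (about 5 of 126)
- h = 25%, s = 0.5: 12.5 points (about 16 of 126)
- any h, s = 1: zero

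The values of h and s are assumed, and the patient's report is taken as the truth. The range shows how the result responds to disagreement; it is not an estimate for this trial.

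**The case against.** Much of the case on the other side is sound.

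- **The investigator's rating is not merely second-hand.** A reader might infer that it must be, because the visit can be by phone, letter or email. Section 12.9 also allows an in-person visit, and the site collects medications, adverse events and the Menorrhagia Impact Questionnaire then. The investigator may have more to go on than the single item. If the rating does simply relay the patient's answer, disagreement should be small.
- **Bias in the device's favour is not established.** The patient is unblinded too, and nothing in the documents shows that investigators rate lighter than patients. An investigator could rate heavier.
- **Comparability with month 12 is not lost through the rater alone, and the fix would not restore it.** Month 12 uses the diary, and diary collection ends there (synopsis, 13.11.2, Table 23-1). The thresholds differ as well: the synopsis labels scores of 75.1 to 99.9 eumenorrhea, which fails at month 12, while the eumenorrhea category in Attachment D does not fail at 24 or 36 months. Inclusion criterion 11b in 11.3.1 mentions diaries through 36 months and needs to be reconciled with the rest.
- **The patient's rating will be reported.** It is a secondary outcome summarised by counts and proportions (17.6), so a marginal difference between raters would be visible.
- **Section 9.3 lists failures and does not define late success.** That every non-failure is a success is an inference, though 17.7 does analyse treatment success at 24 and 36 months.
- **Counting either rater is a choice.** It can only add failures.

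What remains is narrower. A separate table of patient ratings does not enter the failure rate, does not show which women are discordant and does not remove those already failed by intervention. As written, the rule passes over a patient's own report of menorrhagia.

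**Conclusion.** The point holds as a gap in the durability definition. A woman with self-rated heavy bleeding, a lower investigator rating and no intervention is not counted as a failure at 24 or 36 months. Durability success could therefore be overstated, by about 0.8 points per such woman at n = 126 and by nothing if the raters agree. This assumes that late success is read as the absence of failure and that her own report of heavy bleeding should count. Neither the amount nor the net direction of rater disagreement can be taken from the documents.

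The consequence is limited to the descriptive 24- and 36-month results. The 12-month primary endpoint and its test against 66% do not use this rule.

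**What to change.** In section 9.3:

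1. Count a patient-rated High or Heavy on the Patient Global Evaluation at 24 or 36 months as a failure, in addition to the two existing routes.
2. Report the rate under the investigator-only rule beside it as a sensitivity analysis.
3. Cross-tabulate the patient's and the investigator's menstrual-status ratings at each of these visits.

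The change should be made before the 24- and 36-month data are analysed. It takes one sentence in the definition and one table, with no new form, visit or patient burden, because both ratings are already collected. The downside is that the durability rate may come out slightly less favourable. Keeping the investigator's route retains failures that only the investigator records, and the sensitivity analysis lets a reader see how much the choice of rater matters.
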